### 3.3 Secondary Outcomes

1. Pain intensity (NRS) assessments prior to surgery, post-anesthesia care unit (PACU), every 4 to 6 hours beginning on arrival to patient room (to the closet time interval), and hospital discharge up to POD 7.
2. Opioid consumption in daily oral morphine equivalents (OME) – preoperative, intraoperative, PACU stay, beginning on arrival to patient room up to POD 7.
  - a) Patients will be asked to record their daily intake of opioids and pain scores at pre-defined intervals. A research team member will follow-up with study patients to document the patient’s pain score and opioid consumption values for the previous day as well as administer the quality of recovery 15-item questionnaire.
3. Moderate to severe complications during regional anesthesia block placement (inadvertent epidural or subarachnoid injection, local anesthetic systemic toxicity\*, and pneumothorax).
 

*\* Local anesthetic systemic toxicity is suspected if a patient has acute onset of central nervous system changes (tinnitus, metallic taste in mouth, perioral numbness) or cardiovascular changes (bradycardia, hypotension, EKG changes).*
4. Peripheral nerve block catheter-related complications including presence of site infection (tenderness to palpation, erythema, swelling, drainage of pus), hematoma, and local anesthetic systemic toxicity.
5. Inadvertent catheter dislodgement
6. Duration of hospital stay (number of days), in addition to reason for hospital length of stay > 1 night (i.e., social work/disposition, inadequate pain control, nausea/vomiting, other)
7. Postoperative follow-up
  - a. Telephone encounter or office visit to collect NRS pain scores at rest, opioid consumption, questionnaire, and adverse events. Data will be collected for postoperative days 0 to 4; however, patients may be contacted up to postoperative day 7 to collect this information if patients or study staff are unavailable.
8. Questionnaire Forms
  - a) QoR-15
    - i. Quality of Recovery (QoR) 15-item short form patient survey is a validated, reliable, and feasible scoring system evaluating 5 dimensions of health: psychological support, comfort, emotions, physical independence, and pain.
    - ii. Collected preoperatively and POD 1 to 4 via office visit or telephone call.
  - b) Overall benefit of Analgesic Score (OBAS)

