    - i. Validated tool measuring patient’s experience with their postoperative pain regimen. This simple 7 question (Q1 to Q7) scoring system entails a combination of pain intensity, adverse opioid events, and patient satisfaction. The total OBAS score is calculated via ‘sum items Q1 through Q6 and add [4 – score from Q7].’ This score consists of a 29-point scale ranging from 0

(best) to 28 (worst); therefore, lower OBAS scores indicate more analgesic benefit. This will be administered to patients prior to hospital discharge.

9. Cost-benefit analysis
  - a) Examining the cost of each analgesic modality within the overall episode of orthopedic surgical care using the time-driven activity-based costing (TDABC) model, which provides a more accurate representation of true costs by estimating the quantity of time and the cost per unit of time of each resource from preoperative visits to hospital discharge
10. Additional outcome measures for future investigation
  - a) American Shoulder and Elbow Surgeons Standardized Shoulder Assessment Form
    - i. ASES questionnaire will be collected pre-operatively, 3-month, and at 1 year postoperatively via office visit or telephone call. Collected data will be used in a follow-up study.
  - b) Patient-Reported Outcomes Measurement Information System (PROMIS®)
    - i. Already an established and standard questionnaire being collected for all orthopedic surgical patients.

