## 6 Safety Endpoints

These methods are already established procedures in the practice of perioperative pain control for a total shoulder arthroplasty. There is minimal risk of placing a peripheral nerve block. Those risks include infection, bleeding, and/or nerve damage. Patients will be monitored during the perioperative period for any adverse events. During regional anesthesia block placement,

trained sedation nurses or anesthesia personnel (staff physicians, residents, or nurse anesthetists) will be monitoring patients. Patients will be monitored throughout the procedure utilizing the American Society of Anesthesiologists (ASA) standard monitors\*, aspirating for blood or cerebral spinal fluid prior to administration of local anesthetic solution in divided doses, frequent assessment of the patient's well-being via verbal communication, and always having emergency medications and airway equipment readily available. Performing this regional block (ISB) is considered standard in our practice to provide optimal postoperative analgesia.

*\* blood pressure (non-invasive blood pressure cuff cycling every 3 to 5 minutes or continuous arterial blood pressure monitoring placed due to clinical judgment of covering anesthesiologist), 5 lead EKG, continuous pulse-oximetry, and continuous monitoring from operating room anesthesia personnel (if the procedure is performed in the operating room) or frequent assessments by nurses who are trained to care for patients receiving regional anesthesia blocks (if procedure is performed in block room)*

Patients that are not discharged the same day after surgery will be admitted to the regular nursing floors. Vital signs (heart rate, oxygen saturation, and blood pressure) will be captured every 4 to 6 hours or more frequently if the clinical situation dictates in all postoperative orthopedic patients.

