## 8.2 Statistical Methods

The primary outcomes will be pain, as measured by NRS pain intensity scores, and opioid consumption, as measured by milligrams of OME, recorded at 24 hours after surgery. Secondary outcomes will include OBAS, intraoperative and postoperative complications, NRS pain scores, length of hospital stay, and QoR-15 score. The outcomes of pain, opioid consumption, OBAS, and QoR-15 score will be compared between the LB-ISB group and the C-ISB group using two-sample t-tests; if the data are not sufficiently normally distributed, non-parametric Wilcoxon rank sum tests will be used. Since this is a prospective, randomized trial, subjects in the two groups are expected to be similar with respect to their baseline characteristics; therefore, no formal comparisons of baseline data will be performed. However, if it is determined that adjustments need to be made, this will be done using a general linear models framework. Length of stay is likely to be skewed, and thus will be analyzed using the non-parametric Wilcoxon rank sum test. Intraoperative and in-hospital post-operative complications will be analyzed using chi-square tests and logistic regression. The primary analysis will be based on the intent-to-treat

approach, in which subjects will be analyzed in the groups they were randomized to, regardless of the treatment actually received. If appropriate, additional secondary analyses may be undertaken to perform the comparisons on the subjects who completed the study per-protocol, and on an as-treated basis.

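### OBAS is tied to hospital discharge instead of a fixed postoperative time, and discharge timing is itself a post-randomisation outcome compared between arms

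*Combined protocol and SAP*

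**What the plan says.** Section 3.3, item 8(b) describes OBAS as a seven-question instrument scored from 0 (best) to 28 (worst). Its "scoring system entails a combination of pain intensity, adverse opioid events, and patient satisfaction". The only timing instruction is: "This will be administered to patients prior to hospital discharge".

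Discharge timing is expected to vary. Section 6 says: "Patients that are not discharged the same day after surgery will be admitted to the regular nursing floors". The same section refers to study patients who are inpatients and study patients who are outpatients. Section 3.3, item 6 makes length of stay a secondary outcome: "Duration of hospital stay (number of days), in addition to reason for hospital length of stay > 1 night". The reasons it lists are "social work/disposition, inadequate pain control, nausea/vomiting, other".

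Section 8.2 compares OBAS between arms with a two-sample t-test, or a Wilcoxon rank sum test if the data are not sufficiently normal. It treats length of stay as an outcome in its own right: "Length of stay is likely to be skewed, and thus will be analyzed using the non-parametric Wilcoxon rank sum test". It allows adjustment through general linear models, but in the context of baseline comparability.

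The other questionnaire is handled differently. For QoR-15, Section 3.3, item 8(a) says: "Collected preoperatively and POD 1 to 4 via office visit or telephone call".

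**The concern.** A score taken at discharge is taken at a time that depends on how the patient is doing. Two of the protocol's listed reasons for a stay beyond one night, poor pain control and nausea or vomiting, overlap with what OBAS scores. The same experience can therefore move both the score and the moment it is recorded.

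Two things are at stake. First, if discharge timing differs between arms, a timing difference can appear as a difference in analgesic benefit, or hide one. Second, even with identical stay in both arms, the OBAS result would pool answers from different postoperative phases, so it is unclear what quantity is being estimated. That matters here because the two techniques act on different time scales. Section 1.4 describes a liposomal profile with peaks at 1 hour and at 12 to 36 hours, and a catheter infusion planned for 72 hours.

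**Working it through.** **Plan's own figure.** There is none to reproduce. The sample size in Section 8.1 rests on NRS pain and opioid consumption, and nothing is calculated for OBAS. Only the 40 per arm is borrowed from it below.

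**Reading the passages together**

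1. OBAS time equals some time before discharge (3.3, item 8(b)).
2. Discharge may fall on the day of surgery, after one night, or later (Section 6; 3.3, item 6), and stay is expected to be skewed (8.2).
3. Stay is compared between arms and can depend on pain and nausea (3.3, item 6; 8.2).
4. No passage asks for the time from surgery to OBAS to be recorded, and the planned tests have no time term.
5. Table 1 does not settle the day. In the text available its header is broken. OBAS is marked only in the last column, which also carries QoR-15. Because QoR-15 runs from POD 1 to POD 4, that column cannot mean POD 0 alone, and it may exclude POD 0.

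**Illustration 1, in OBAS points (all inputs assumed).** Suppose there is no treatment effect at any fixed time. Let mean OBAS be m0 if answered on the evening of surgery and m1 if answered on POD 1, the same in both arms, and let p be the proportion discharged the same day. Each arm's mean is p × m0 + (1 − p) × m1, so

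spurious difference = (p_A − p_B) × (m0 − m1).

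With a difference in p of 0.20:

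- change of 2 points: 0.20 × 2 = 0.4
- change of 3 points: 0.20 × 3 = 0.6
- change of 4 points: 0.20 × 4 = 0.8

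As a share of the scale: 0.4/28 = 1.4% and 0.8/28 = 2.9%.

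**Illustration 2, in SD units (all inputs assumed except 40 per arm).** Let OBAS drift by b SD per day and let mean assessment day differ by d days between arms. Then bias = b × d SD. In standard-error units the shift is b × d / √(2/40) = b × d / 0.2236. The two-sided 5% rejection rate with no true effect is Φ(shift − 1.96) + Φ(−shift − 1.96).

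| Drift b (SD/day) | d = 0 | d = 0.25 day | d = 0.5 day |
|---|---|---|---|
| 0.25 | 5.0% | 5.9% | 8.6% |
| 0.50 | 5.0% | 8.6% | 20.1% |
| 0.75 | 5.0% | 13.4% | 38.9% |
| 1.00 | 5.0% | 20.1% | 60.9% |

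Worked cell: b = 0.5, d = 0.5 gives a bias of 0.25 SD, a shift of 0.25/0.2236 = 1.118, and a rejection rate of 20.1%.

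The first column shows the condition: with no difference between arms in mean assessment day, the test keeps its 5% level whatever the drift. A common assessment time sets d to zero.

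**The case against.** A rating at discharge is a coherent choice for a summary of the patient's experience with the pain regimen, and it lets patients complete the form in hospital. No primary conclusion rests on OBAS. Comparisons at defined times are already planned: NRS and opioid consumption at 24 hours, repeated NRS, daily opioid totals, and QoR-15 on POD 1 to 4. Asking for a reason only when the stay exceeds one night suggests that stays are usually short, which would narrow the spread. All of this stands and limits the importance of the point. It does not remove it: the protocol does not define OBAS as an end-of-stay summary, and such a summary would still cover unequal periods.

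Three stronger readings are tempting, and the documents do not support them.

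- A reader might infer that same-day patients certainly answer OBAS within hours of the block. The discharge wording points that way, but the broken Table 1 may place OBAS after POD 0, so this is uncertain.
- A reader might infer that the catheter lengthens stay and so separates the arms. Catheter care is not among the listed reasons for a longer stay, and Sections 5.2 and 6 provide for discharge with the ambulatory pump and follow-up.
- A reader might take the illustrative figures as estimates of bias. They rest on assumed inputs.

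Nor is the planned analysis only a t-test. The Wilcoxon alternative is there, although it does not correct for unequal timing either.

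**Conclusion.** The point holds as a design weakness in one secondary outcome. OBAS has no fixed postoperative time. Its timing follows a post-randomisation variable that can depend on the same pain and nausea that OBAS measures, and the planned comparison does not allow for that.

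The size is unknown. The documents do not show that stay will differ by arm. They give no OBAS standard deviation, time course, minimal important difference or discharge distribution. The 0.4 to 0.8 points and the rejection rates in the table illustrate the mechanism under stated assumptions. If nearly all patients leave at about the same time, the effect is small. If mean assessment time is equal between arms, the false-positive rate stays at 5%, although the score still mixes different phases of recovery.

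Adjusting afterwards for length of stay or time to OBAS is not a clean remedy, because both are post-randomisation and may be affected by treatment. The remedy belongs in data collection. I would class this as a cheap improvement; it does not threaten the trial's main conclusions.

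**What to change.** In Section 3.3, item 8(b), replace the discharge-based timing with collection on POD 1 in every patient, at the contact where QoR-15 is already taken, in person or by telephone, whatever the discharge status. This matches the POD 1 timing of the primary outcomes. Reconcile the OBAS row of Table 1 with the new wording.

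Record the actual date and time of completion and the mode (in person or telephone). This is needed because Section 3.3, item 7 lets contacts slip to as late as POD 7, so naming POD 1 does not by itself guarantee a common time.

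Cost: a line or two in the protocol, the table entry, and two fields on the case report form, with no new contact. Downside: some patients will answer by telephone, so mode will partly follow discharge status, and a few late or missing responses are possible.

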## 4 Subject Selection Enrollment and Withdrawal

### 4.1 Inclusion Criteria

1. Adult patients with an American Society of Anesthesiologists (ASA) physiological status I-III
2. Patients presenting for unilateral primary total shoulder arthroplasty (includes anatomic and reverse total shoulder arthroplasty).
3. Patients 18 years of age and older
4. Able to provide informed consent for him or herself

### 4.2 Exclusion Criteria

1. Chronic pain syndromes
2. Chronic opioid use (>1 month) with OME >5 mg/day OR acute opioid use (< 1 month) with OME > 30 mg/day.
3. Body mass index (BMI) > 45 kg/m^2
4. Severe drug allergy\* to medications used in this study, including non-steroidal anti-inflammatory drugs (i.e. celecoxib) and local anesthetics.
  - *\*defined as an immune reaction resulting in shortness of breath, hives, anaphylaxis, wheezing, and fever*
5. Personal or family history of malignant hyperthermia.
6. Major systemic medical problems such as:
  - Pre-existing severe renal disorder defined as glomerular filtration rate (GFR) <50 units/m^2 (if labs are available), currently on dialysis, or highly suspected based on history.

- Severe hepatic disorder defined as current or past diagnosis of acute/subacute necrosis of liver, acute hepatic failure, chronic liver disease, cirrhosis (primary biliary cirrhosis), chronic hepatitis/toxic hepatitis, liver abscess, hepatic coma, hepatorenal syndrome, other disorders of liver
  - Pre-existing medical history of moderate to severe pulmonary disease requiring medical therapy (obstructive and/or restrictive), use of home oxygen, preoperative baseline oxygen saturation < 93% on room air.
  - History of contralateral hemidiaphragm dysfunction (e.g., paralysis) or phrenic nerve injury.
7. Contraindication to a regional anesthesia technique (e.g., preexisting neuropathy+ in the operative extremity, coagulopathy, sepsis, infection at site of injection, uncooperative, and refusal).
    - + *pre-existing neuropathy includes sensory and/or motor deficits due to nerve insult of surgical extremity, radicular symptoms of surgical extremity, history of unresolved brachial plexus injury/brachial plexopathy, and tumors of the brachial plexus. Patients with nerve compression distal to site of surgery, such as history of carpal tunnel syndrome or cubital tunnel syndrome, are NOT considered contraindications to regional anesthesia.*
  8. Known to be currently pregnant or actively breastfeeding++
    - ++ *All surgical patients are currently screened using a standardized Pregnancy Assessment tool (<http://mayoweb.mayo.edu/sp-forms/mc8800-mc8899/mc8801-161.pdf>)*
  9. Impaired cognition (e.g. Alzheimer's disease, moderate to severe dementia, encephalopathy)
  10. Non-English speaking

### 4.3 *Early Withdrawal of Subjects*

#### 4.3.1 **When and How to Withdraw Subjects**

If the patient is unable to comply with the study protocol or they wish to withdraw from the study their participation in the study will be terminated. Furthermore, if the placement of the peripheral nerve blocks cannot be performed, if an unanticipated reoperation is performed (during the same hospital stay), if an unanticipated complication unrelated to the study (e.g. pulmonary embolism, myocardial ischemia) where patients are unable to participate in study protocol, or if the patient remains intubated and sedated postoperatively for greater than one day, the patient will be terminated from the study. If the interscalene nerve block catheter becomes occluded or is pulled out prematurely, patients will remain in the study as our primary analysis will be performed based on the intention to treat.

In order to account for 10% dropout, which includes patients terminated from the study, a total sample-size of N = 88 (44 per group) is proposed. Follow-up will not be performed for patients terminated from the study.

If the patient chooses not to participate, he or she will be provided the current perioperative care plan in place by the surgeon which will include various pain management options regardless of participation.

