\*Patients may be contacted up to postoperative day 7 to collect data depending on availability of patient and study staff during follow-up encounters.

Office Visit

Study Recruitment  
Inclusion/exclusion criteria  
Discuss Study  
Consent  
  
74 Patients

Pre-OP

Randomize on Day of Surgery  
Dynamic Allocation  
  
1:1 LB-ISB vs. C-ISB

LB-ISB  
37 patients

C-ISB  
37 patients

Intra-OP

Shoulder Surgery

Post-OP

Postoperative Period  
Up to POD 7  
*(dependent on follow-up availability)*

- Capture:
- Pain Scores
  - Opioid Consumption
  - Length of Hospital Stay
  - Adverse Events
  - Quality of recovery Score
  - Overall Benefit of Analgesic Score
  - TDABC

Figure 1. Diagram of patient flow from recruitment to outpatient follow-up

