#### **4.3.2 Data Collection and Follow-up for Withdrawn Subjects**

Patients who voluntarily withdraw from the study, are terminated due to unforeseen circumstances such as reoperation, or if intubated and sedated postoperatively for greater than one day, will have their data collected in the peri-operative and follow-up periods up to the point of termination. Our primary analysis will be performed based on the intention to treat. A subgroup analysis will also be performed on patients who received the allocated treatment as per the planned protocol.

The safety profile for liposomal bupivacaine has been assessed in previous studies as mentioned in Section 1.3, and the primary outcome for this study involves assessing its analgesic efficacy compared to other standard methods of regional anesthesia acute pain management techniques for patients undergoing total shoulder arthroplasty. Survival data for liposomal bupivacaine will not be assessed in this study; thus, we will plan to exclude data after a patient's termination/withdrawal date.

If the patient chooses not to participate, he or she will be provided the current perioperative care plan in place by the surgeon and will include various pain management options regardless of participation.

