## **7.2 Treatment Regimen**

Patients randomized to LB-ISB will receive a preoperative single-injection interscalene block for pain management following primary total shoulder arthroplasty. The solution administered will contain 5 mL of bupivacaine 0.5% (25 mg) along with 10 mL of liposomal bupivacaine (133 mg), which conforms to manufacture recommended guidelines.

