### **8.5 *Subject Population(s) for Analysis***

Our primary analysis will be performed based on the intention-to-treat. Therefore, any subject randomized into the study and undergoing the planned surgical procedure, regardless of whether they received a liposomal bupivacaine single injection interscalene blockade or a continuous interscalene nerve block, will be included in the primary analysis in the group they were randomized to. If appropriate, additional subgroup analyses may be performed on patients who received the allocated treatment as per the planned protocol, and on an as-treated basis.

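### Patients whose block cannot be placed are terminated without follow-up, so the intention-to-treat primary analysis that includes them has no 24-hour outcomes for them

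*Combined protocol and SAP*

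**What the plan says.** **Termination.** Section 4.3.1 lists several reasons for ending a patient's participation. One applies in either arm: "if the placement of the peripheral nerve blocks cannot be performed". For all terminated patients it adds: "Follow-up will not be performed for patients terminated from the study". Section 4.3.2, after noting that survival will not be assessed, says "thus, we will plan to exclude data after" the date of termination or withdrawal.

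**Exception.** The same paragraph of 4.3.1 treats a later technical failure differently: "If the interscalene nerve block catheter becomes occluded or is pulled out prematurely, patients will remain in the study". The reason given is that the primary analysis is by intention to treat.

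**Timing.** Figure 1 in section 3.1 has "Randomize on Day of Surgery". Section 5.1 describes the block in both arms as part of the preoperative plan, and section 7.2 says patients in the liposomal arm "will receive a preoperative single-injection interscalene block for pain management". Section 8.2 sets the primary outcomes, NRS pain and oral morphine equivalents (OME), at 24 hours after surgery.

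**Analysis set.** Section 8.5 includes in the primary analysis "any subject randomized into the study and undergoing the planned surgical procedure, regardless of whether they received a liposomal bupivacaine single injection interscalene blockade", with the continuous technique named as the other possibility, each in the randomised group. Section 8.2 says assignment governs whatever treatment was received. Section 8.4 says the same whatever the sequence of treatment.

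**Missing data.** Section 8.4 provides for a review, by study group, of patients with and without data. It allows adjustment if judged necessary but names no method. Section 4.3.1 sizes the trial "In order to account for 10% dropout, which includes patients terminated from the study", giving 88 (44 per group).

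**The concern.** Sections 4.3 and 8.5 cannot both be carried out. One requires these patients in the primary comparison; the other stops collection of the values needed to include them. The planned t-test or Wilcoxon test uses observed values, and no imputation is specified. Unless someone intervenes, the analysis will therefore contain only patients who were not terminated.

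That exclusion happens after randomisation and depends on whether the assigned technique could be delivered, which is part of what separates the two strategies. Section 1.1 names technical difficulty of catheter placement as a drawback of the continuous block, so equal failure in the two arms cannot be assumed. The trial is unblinded, so the staff who judge that a block cannot be placed know the assignment. If failures, or the pain that follows them, differ between arms, the comparison is biased.

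The 10% allowance adds patients to protect power. It does not recover the outcomes of those removed.

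**Working it through.** **1. Sequence for a failed placement**

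| Step | Source | Consequence |
|---|---|---|
| Randomised on the day of surgery | 3.1, Figure 1 | Belongs to an arm |
| Block attempted before surgery, cannot be placed | 5.1, 7.2 | Termination under 4.3.1 |
| No follow-up; later data excluded | 4.3.1, 4.3.2 | Nothing collected from here on |
| Planned surgery takes place | 8.5 | Meets the definition of the primary set |
| NRS and OME due at 24 hours | 8.2 | Missing by design |

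Nothing in the documents says that failed placement cancels surgery. A patient whose surgery was cancelled would fall outside 8.5.

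**2. The plan's own sample size**

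Inputs from 8.1: SDs 2.4 and 2.3 (NRS), 23.6 and 25.1 mg (OME); targets 1.5 points and 20 mg; two-sided alpha 0.05; 80% power.

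- NRS: pooled SD = √((2.4² + 2.3²)/2) = 2.351. n = 2 × (1.96 + 0.84)² × 2.351²/1.5² gives 39 per arm. The t-test version gives 39.5, so 40. Power at 40 per arm is 80.5%.
- OME: pooled SD 24.36; power at 40 per arm is 95.2%.
- 80 × 1.10 = 88, as stated.

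The figure reproduces. NRS power is 82.3% with 44 against 40 analysed and 80.1% with 44 against 36. Power is not the problem; bias is.

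**3. Illustration of bias**

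The documents give neither failure counts nor outcomes after failure, so both are assumed. Suppose k of 44 patients in one arm are terminated and their 24-hour value would have averaged D above that arm's remaining patients. The observed arm mean is then too low by (k/44) × D, which favours the arm with the failures. With failures in both arms and the same D, the shift is (difference in k)/44 × D.

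False-positive rate = P(|Z + shift/SE| > 1.96), when the true difference over all randomised patients is zero. With 40 per arm:

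- NRS: SE = √(2.4²/40 + 2.3²/40) = 0.526
- OME: SE = √(23.6²/40 + 25.1²/40) = 5.45

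| Failures, one arm only | NRS shift (D = 2 / 4) | False-positive rate | OME shift (D = 20 / 40 mg) | False-positive rate |
|---|---|---|---|---|
| 1 | 0.05 / 0.09 | 5.1 / 5.3% | 0.5 / 0.9 mg | 5.1 / 5.3% |
| 2 | 0.09 / 0.18 | 5.3 / 6.4% | 0.9 / 1.8 mg | 5.3 / 6.3% |
| 4 | 0.18 / 0.36 | 6.4 / 10.6% | 1.8 / 3.6 mg | 6.3 / 10.2% |
| 6 | 0.27 / 0.55 | 8.1 / 18.0% | 2.7 / 5.5 mg | 7.9 / 17.0% |

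Four failures in one arm and two in the other give the row for 2. Equal failures with equal D give zero shift and 5.0%. Using the patients actually left (44 against 40), the four-failure maxima are 10.9% for NRS and 10.5% for OME.

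**The case against.** **Section 8.5 can be read more narrowly.** Its sentence goes on to name the continuous block as the alternative. It may therefore mean whichever of the two blocks was received, leaving patients with no block unaddressed. This is a fair reading of that sentence alone. It still conflicts with 8.2 and 8.4, which set no such limit, and the text would need clarifying in any case.

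**Section 8.4 already plans a by-arm review of missingness.** It does, and it permits adjustment. A review can describe the gap but cannot supply outcomes that 4.3 says not to collect, and no method is fixed in advance.

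**The trigger may be rare, and similar in both arms.** Section 4.3.1 does not say whether a patient whose catheter cannot be sited, but who can be injected, counts as a failed placement. If only complete failure counts, both arms share the same ultrasound-guided access, nerve stimulation is allowed when imaging is poor, and patients with contraindications are excluded at entry. A large imbalance is then less obvious. This stands as a limit on the likely size of the bias, and the ambiguity itself needs resolving.

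**The illustration is built on assumptions.** This also stands. Four failures would use one arm's whole dropout allowance (44 to 40), and six would exceed it. The false-positive rate further assumes no difference over all randomised patients. With failures in one arm only, that means the successfully blocked patients in that arm do better by just enough to offset them.

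**Conclusion.** The concern holds. The conflict between 4.3 and 8.5 is in the text, and it is clear how it removes randomised patients from the primary comparison. Confidence in that is high. A demonstrated bias is not claimed: its size and direction cannot be established from the documents. It is about zero if failures and their excess pain are balanced. Under the assumed range of one to four failures in one arm, it is 3% to 24% of the NRS target and 2% to 18% of the OME target. The conclusion rests on the contradiction, not on those figures.

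For safety the gap is small. Sections 9.1 and 9.2 still require follow-up of related unresolved events and of serious events, so only later non-serious events are left unclear.

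This should be fixed, and early, because pain scores that are not collected may not be recoverable later.

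**What to change.** 1. In 4.3, separate ending study participation from ending data collection. For every randomised patient who has the planned surgery and has not withdrawn consent, including failed placement, continue to collect 24-hour NRS, OME and adverse events from the medical record and the contacts already planned. Analyse them in the assigned arm.
2. Limit the no-follow-up sentence in 4.3.1 and the data exclusion in 4.3.2 to withdrawal of consent. The same sentences currently also cover reoperation, unrelated complications and prolonged intubation.
3. State what counts as failed placement in each arm, and report its number and reasons by arm.
4. In 8.4, name one method for 24-hour values that still cannot be obtained (multiple imputation within arm is one option), plus a sensitivity analysis that sets missing values worse by a stated amount.
5. Reconcile 4.3.1 and 4.3.2 with 8.2, 8.4 and 8.5, and with the adverse-event follow-up in sections 6, 9.1 and 9.2.

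Relabelling the primary set as modified intention to treat would make the text consistent but would leave the exclusion in place.

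The cost is a short amendment to 4.3, 8.4 and the matching wording, and data collection on a few more patients. N stays 88 and no procedure is added.
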